7. STUDY POPULATION

7.1 Eligibility criteria

Participants fulfilling all of the following inclusion criteria are eligible for the study, for example:

- Informed Consent as documented by signature
- Need for thoracoscopic procedures under general anaesthesia,
- American Society of Anaesthesiologists [ASA] physical status class I to III.
- Age \geq 18 years

The presence of any one of the following exclusion criteria will lead to exclusion of the participant, for example:

- Contraindications to the class of drugs under study, e.g. known hypersensitivity or allergy to class of drugs or the investigational product,
- Contraindications to self-administration of opioids,
- Women who are pregnant or breast feeding; a pregnancy test will be performed
- Steroid therapy,
- Chronic pain therapy,
- Atrioventricular block grade II to III,
- Congestive heart failure,
- Liver insufficiency,
- Known or suspected non-compliance, drug or alcohol abuse,
- Inability to follow the procedures of the study, e.g. due to language problems, psychological disorders, dementia, etc. of the participant,
- Participation in another study with investigational drug within the 30 days preceding and during the present study,
- Enrolment of the investigator, his/her family members, employees and other dependent persons,

7.2 Recruitment and screening

The patients will be recruited by the thoracic surgeons in the Department of Thoracic Surgery, University Hospital Basel. All thoracic surgeons will be informed about the study. Typically, patients are first seen in the ambulatory clinic or in the tumour board. Patients who need to undergo a thoracoscopic procedure will be approached and informed about the study. An informed consent will be obtained and the patients will be screened for eligibility.

The study should take about four years to be completed. Based on our previous experience we expected the presentation of 200 patients per year with the need for elective thoracoscopic procedures. From our experience, we initially expected about 70% of these patients to be eligible and consent to study participation. We therefore calculated a 2 year recruitment period, i. e. a study-duration of one year as additional 6 months for the last follow up. In the meantime we identified an eligibility and consent to study participation of 30 % of our patients. For this reason and due to a not correct monitoring of the storage temperature of the IMP we have to include further patients and extend the recruitment period (study duration) to 3,5 years and additional 6 months for the last follow-up. The deviation from the storage temperature specified in the product information (RT, 15 – 25°C) of IMP (average 26.2°C; 19.2 – 27.9°C) lasted 6 months (20.05.2020 – 09.11.2020). Before May 2020 storage temperature of the IMP was not monitored. We consulted the Manufacturer (Sintetica SA) concerning this issue and got the information that in-house studies (Sintetica SA), which are not available for clients, show, that the IMP will be stable for 6 months at 40°C without influencing IMP quality. Since the initiation of the trial neither events due to safety reasons occurred nor supplementary medical intervention were necessary due to application of IMP stored under elevated temperature. No SAE occurred due to application of IMP. For this reason a threat for study patients can be excluded. Since 13.11.2020 the IMP is stored as in product information described temperature.

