
Study Product / Intervention:
	
Lidocaine arm: Intravenous [IV bolus] injection of lidocaine 1,5 mg/kg before intubation and at least 30 minutes before incision, followed by a continuous IV infusion of lidocaine 3,0 mg/kg/h, until 2 hours after skin closure. The patient can be transferred to the ward after the PACU discharge criteria are met. PACU discharge criteria are standardized for the University Hospital Basel.

Control Intervention (if applicable):
	
Placebo arm: Likewise procedure as in the lidocaine arm, but with placebo solution (NaCl 0,9%).

Number of Participants with Rationale:
	
113
 
For this study, 113 patients should be recruited to ensure 42 evaluable patients, assuming a drop-out rate of 25 %. This sample size allows with a power of 0.8 to show a group difference in the SIA score assuming a daily reduction in morphine consumption due to lidocaine of 2 mg and a reduction in the pain score of 1.5 points.
 
We have to expand the 59 to 113 patients since we intend to include in our final statistical analysis only patients who are treated with lidocaine stored as described in the product information. The storage temperature is correctly monitored since November 2020.

Study Duration:
	
The study should take about 4 years to be completed.

[figure not shown]
Study Schedule:	First-Participant-In: April 2019 Last-Participant-Out: anticipated December 2022

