11.3 Interim analysis to update sample size estimation

As planned in the study protocol, we updated our sample size estimate based on the data when at least 10 evaluable patients per arm are recruited. Specifically, the sample size re-estimation was performed when a total of 34 were recruited with 15 patients in the smallest treatment arm. Note that this sample size re-estimation was performed on the data that is not used for the final analysis, for reasons discussed above concerning the layering temperature of the lidocaine. We strongly believe that the information used for this sample size re-estimation - the variability of the outcome in the treatment arms - is not meaningfully influenced by the fact that in the lidocaine arm, the medicament temperature was not monitored correctly. Therefore, we deem the estimate of the variability generalizable to the new data which is collected now monitoring is assured.

We resampled data from the first 34 patients. Note that in the resampling procedure, the pain and morphine value of each patient were kept together as a pair, so that the correlation between both variables was kept intact.

Note that the statistician performing this analysis was blind to the treatment arm labels during the analyses. For both pain and morphine, the arm-means were subtracted from each value. This has two advantages: 1) If we would simply resample the raw values across arms, our simulation would be

based on too large a variance if there truly were a difference between the treatment arms. 2) The subtraction of the arm means assures that the data analyst is really blind to eventual effects in the data while performing the sample size re-estimation.

The result of the resampling analysis is shown in Figure 1. The figure shows the total number of evaluable patients (both arms together, on the y-axis) required to reach different levels of power (separate lines), given a range of true effect sizes in terms of θ (x-axis). The Figure is based on samples with replacement from the interim data set, where in each simulation, the treatment effect on morphine use was set to θ and the effect on pain to $0.75 \cdot \theta$.

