11.5.3 Safety analysis

Safety will be assessed via a rigorous and detailed examination of serious adverse events. The proportion of participants with an adverse event or a serious adverse event will be estimated by trial arm, and reported together with 95%-confidence intervals, calculated according to Blaker (2000)¹⁵.

All safety analyses will be performed on the FAS.

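### Section 7.2 declares a threat from mis-stored lidocaine excluded without giving the number exposed, and the protocol does not settle whether those patients enter the safety analysis

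*Protocol*

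**What the plan says.** Section 7.2 reports that the lidocaine was kept outside its labelled range of 15 to 25°C ("average 26.2°C; 19.2 – 27.9°C) lasted 6 months (20.05.2020 – 09.11.2020"), and adds: "Before May 2020 storage temperature of the IMP was not monitored". It then gives three grounds for reassurance:

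- The manufacturer reported that in-house studies, which clients cannot see, "show, that the IMP will be stable for 6 months at 40°C without influencing IMP quality".
- Since the trial began, "neither events due to safety reasons occurred nor supplementary medical intervention were necessary due to application of IMP stored under elevated temperature".
- The final ground and the conclusion: "No SAE occurred due to application of IMP. For this reason a threat for study patients can be excluded".

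Storage is reported as correct from 13.11.2020.

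The number of patients who received this lidocaine is not given. The nearest figure is in section 11.3: "the sample size re-estimation was performed when a total of 34 were recruited with 15 patients in the smallest treatment arm". That section adds that these data will not be used for the final analysis, because of the storage problem. The synopsis (Number of Participants with Rationale) gives the rule in general terms: "we intend to include in our final statistical analysis only patients who are treated with lidocaine stored as described in the product information". It raises the recruitment target from 59 to 113 for that reason.

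Section 11.5.3 plans adverse event and SAE proportions by arm, "reported together with 95%-confidence intervals, calculated according to Blaker (2000"), with all safety analyses on the FAS. The abbreviation list expands FAS as full analysis data set, but the protocol does not say who belongs to it.

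**The concern.** Excluding a threat is a strong conclusion. To reach it from clinical data one needs a denominator, an upper limit and a rate regarded as tolerable, and section 7.2 gives none of these. The zero is also a count of events judged to be caused by the drug, with no figure by arm beside it. Safety objectives and outcomes (4.4, 5.4) and the adverse event assessment (9.2.4.1) are marked not applicable, as is a data safety monitoring committee (1.6).

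The statement stands in a document submitted to the ethics committee and the authority, and it accounts for how a drug-quality deviation was handled. The trial's own safety table could put a limit on the risk in the patients concerned. If the synopsis rule is applied as worded, those patients never reach that table.

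**Working it through.** The protocol gives no rate, limit or denominator for this statement, so there is no figure of its own to reproduce. The steps below set out what its other figures allow.

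**1. How many lidocaine patients could be involved**

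- Section 11.3: 34 recruited, 15 in the smaller arm, so 34 − 15 = 19 in the larger. The lidocaine arm is 15 or 19. These are recruited patients; the number dosed is not stated.
- Synopsis and section 11.3: the target rises by 113 − 59 = 54. If those 54 replace the patients treated before storage was corrected, 1:1 allocation (section 6.2.1) gives 54 / 2 = 27 on lidocaine. This is an inference from planning targets.
- The number given lidocaine within the measured window (20.05.2020 to 09.11.2020) is not stated and may be below 15.

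**2. What zero events can exclude**

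With 0 events in n patients, the one-sided 95 % upper limit is 1 − 0.05^(1/n). The two-sided exact (Clopper-Pearson) limit is 1 − 0.025^(1/n). If the true rate is p, the chance of seeing no event is (1 − p)^n. The confidence level is my assumption, since section 7.2 names none. Clopper-Pearson stands in for the Blaker interval planned in 11.5.3.

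| Lidocaine patients, n | One-sided 95 % limit | Two-sided 95 % limit | P(no event) if p = 5 % | P(no event) if p = 10 % |
|---|---|---|---|---|
| 15 | 18.1 % | 21.8 % | 46 % | 21 % |
| 19 | 14.6 % | 17.6 % | 38 % | 14 % |
| 27 | 10.5 % | 12.8 % | 25 % | 6 % |

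With only 10 patients the one-sided limit would be 25.9 %.

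**3. What the stability information covers**

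- Measured deviation: 20.05.2020 to 09.11.2020 is 173 days, and 173 / 30.44 = 5.7 months. The recorded maximum was 27.9°C. Taken at face value, 6 months at 40°C covers this.
- Unmonitored period: the first participant entered in April 2019. From 01.04.2019 to 20.05.2020 is 415 days, and 415 / 30.44 = 13.6 months at most. There is no temperature record for this time. The protocol does not say how long any unit used was in storage, so the 6-month figure can be neither matched to this period nor ruled out for it.

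**4. Whether the affected patients enter the safety analysis**

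- Synopsis: the final statistical analysis includes only patients treated with correctly stored lidocaine, and efficacy is not named as the limit of that rule.
- Section 11.3: the data from the first 34 patients are not used in the final analysis.
- Section 11.5.3: all safety analyses are on the FAS, with no mention of storage.

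On its face the synopsis removes these patients from safety as well. A full analysis set in its ordinary sense would keep them. Nothing in the protocol reconciles the two.

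**The case against.** The strongest reply is that section 7.2 does not rest on the SAE count alone. The stability information bears most directly on a storage question, and the highest recorded temperature was about 12°C below the tested one (40 − 27.9 = 12.1). That stands, and it would be wrong to present the zero count as the only ground. However, the sponsor could not see the stability data, and they cannot be tied to a period without temperature records. The absence of other events comes from the same small, unstated group.

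A reader might infer from the table that faulty storage could have raised the SAE rate by 10 to 18 percentage points. The documents do not support that. The limit applies to any lidocaine-related SAE and would be the same for correctly stored drug with the same zero count. Nothing here suggests that harm is likely.

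A reader might also infer that patients received lidocaine kept for more than a year outside its range. The protocol does not say so. Section 8.8 describes lidocaine as a standard hospital product in general use, so 13 months without monitoring is not 13 months of exposure for any unit. Section 7.2 also discloses the unmonitored period openly.

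Finally, it cannot be claimed that the affected patients will certainly be missing from the safety table. The synopsis sentence belongs to a sample-size rationale built on the SIA score, and the FAS may be defined in a statistical analysis plan not at hand. SAEs are collected throughout the study (10.1) and annual safety reports are planned (10.1.2). What remains is that the protocol's wording points both ways.

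**Conclusion.** The concern holds in a limited form. No related SAE in an assumed 15 to 27 lidocaine patients leaves a related-SAE rate of up to 18.1 % to 10.5 % (one-sided 95 %), or 21.8 % to 12.8 % (two-sided), compatible with the data. The other two grounds do not close the gap, so the conclusion in 7.2 is stronger than its evidence. These figures assume that the denominators inferred from section 11.3 and the synopsis are about right, that those recruited were dosed, and that every event was attributed correctly. A smaller exposed group would widen the limits.

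The part with a consequence for the analysis is the conflict between the synopsis and section 11.3 on one side and section 11.5.3 on the other. As written, the plan can drop from the safety analysis the very patients about whom the safety claim is made. No efficacy or sample-size figure depends on this. The storage fault had been corrected before version 3.2 of the protocol (14.01.2021), so the weight of the point is moderate.

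**What to change.** 1. **Section 7.2.** Replace the sentence that excludes a threat with a bounded statement: the number of SAEs attributed to the drug, the actual number of lidocaine patients treated before 13.11.2020, and the upper 95 % confidence limit. Add that these data do not by themselves exclude an increased risk, and that the full length of the deviation is unknown because of the unmonitored period the section already reports.

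2. **Synopsis and section 11.5.3.** State that the restriction to correctly stored lidocaine applies to the efficacy analysis only. State that all dosed patients, including those treated before 13.11.2020, stay in the safety analysis by arm, with the Blaker intervals already planned. A split by storage period is optional.

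The cost is a few sentences and, if the split is made, one small extra table. No further patients or procedures are needed. The drawback is a less reassuring safety statement with a wide interval.

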7.3 Assignment to study groups

The assignment of each participant to LA or PA group is done by the anaesthesiologist, dedicated study nurse of the department or thoracic surgeon during the treatment preparation. The randomization procedure is described in section 6.2.1.

7.4 Criteria for withdrawal / discontinuation of participants

Patients have the right to withdraw from the trial at any time for any reason and without indicating a reason. The patient can be withdrawn from the study by the PI or its delegates for the following reasons:

- Withdrawal of informed consent
- Non-compliance
- The thoracoscopic procedure is converted to a thoracotomic procedure

8. STUDY INTERVENTION

8.1 Identity of Investigational Products (treatment)

8.1.1 Experimental Intervention (treatment)

Lidocaine is a sterile non pyrogenic solution that contains a local anaesthetic agent and is administered parenterally by continuous infusion.

In addition, it is also an antiarrhythmic drug. It was the first amino amide-type local anaesthetic in 1943.

Lidocaine is rapidly metabolized by the liver, and less than 10% of a dose is excreted unchanged in the urine. Oxidative N dealkylation, a major pathway of metabolism, results in the metabolites monoethylglycinexylidide and glycinexylidide. The pharmacological/toxicological activities of these metabolites are similar to, but less potent than, lidocaine. The primary metabolite in urine is a conjugate of 4-hydroxy-2,6,-dimethylaniline. The elimination half-life of lidocaine following an intravenous bolus injection is typically 1.5 to 2 hours. There are data that indicate that the half-life may be 3 hours or longer following infusion of greater than 24 -hours¹².

The perioperative IV administration regimen of lidocaine will be as follows: 1,5 mg/kg IV induction bolus dose followed by continuous infusion of 3,0 mg/kg/h, until 2 hours after skin closure. Signs of toxicity (for central nervous system like somnolence, tinnitus, slurred speech, cramps, visual disturbances, seizures and for the heart like negative inotropia, bradycardia, vasodilation) may start to appear at plasma levels of 5 µg/ml. However, it usually takes up to 10 µg/ml of lidocaine plasma levels for these signs to appear. Using the regimen of lidocaine administration of 1,5 mg/kg, bolus dose, followed by continuous infusion at 3,0 mg/kg/h, the following plasma concentrations of lidocaine were observed: 1,9 ± 0,7 µg/ml¹¹ and 2,1 ± 0,4 µg/ml⁷, respectively.

8.1.2 Control Intervention (standard/routine/comparator treatment)

Our control intervention is the placebo, NaCl.

A NaCl intravenous solution is a solution of sodium chloride in water for injection. It serves as a substitute for water, sodium and chloride, and can be used as fluid replacement in hyponatremia, hypochloremia and as a carrier solution for active pharmaceutical ingredients.

Sodium chloride (NaCl, Mr: 58,44 g/mol) is a white crystalline powder, colorless crystals or white pearls. It has a salty taste and is readily soluble in water. The solution is administered intravenously as an infusion. NaCl infusion solutions are well tolerated in general. Possible adverse effects include, as with other infusions, venous irritation and thrombophlebitis.

8.1.3 Packaging, Labelling and Supply (re-supply)

After randomisation process, the anaesthesiologist or dedicated study nurse of the department that is not participating in surgery (according to the delegation log) will label the IMPs with Patient ID and Chargen/Batchnumber on the day before surgery and will store the IMP max 24 hours at 6°C in a designated cooler until administration. Medication is available in the University Hospital Basel as it is used in several other indications.

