2.9 Early termination of the study

The Sponsor-Investigator may terminate the study prematurely according to certain circumstances, for example:

- ethical concerns,
- insufficient participant recruitment,
- when the safety of the participants is doubtful or at risk, respectively,
- alterations in accepted clinical practice that make the continuation of a clinical trial unwise,
- early evidence of benefit or harm of the experimental intervention

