6.2.2 Blinding procedures

The treatment assignment is done by the randomization algorithm and recorded in the EDC software secuTrial. The access to secuTrial is password protected and restricted to the trained staff only. The randomizing anaesthesiologist, dedicated study nurse of the department or thoracic surgeon will not be involved in patient care or patient assessment.

The Lidocaine/placebo will be prepared after patient inclusion and randomization in syringes marked with patients study number by the anaesthesiologist or dedicated study nurse of the department that is not participating in surgery (according to the delegation log) just before surgery and storage in a designated cooler until administered. The IMPs data will be recorded in the dispensing log accessible for a potential emergency unblinding.

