6.3 Unblinding Procedures (Code break)

The anaesthesiologist or thoracic surgeon can unblind each participant at any time by extracting the treatment assignment from the records in the EDC software. The anaesthesiologist or thoracic surgeon will report to the sponsor/principal investigator and document the unblinding process. Unblinding will occur if there are any indications of an allergic reaction, and/or the patients general and/or neurological condition worsens, and/or there are signs of adverse reaction to the medication.

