9.3.4 Data of patient-controlled analgesia (PCA)

- Total morphine consumption (mg)
- Total PCA requests
- Positive PCA requests
- Negative PCA requests
- Pain intensity (VAS Score) – with coughing and when immobile
- Riker sedation agitation scale¹⁸PONV [nausea, present or not; vomiting, number of events]
- Adverse events of lidocaine infusion (light headedness, drowsiness, perioral numbness, visual disturbances, metal taste)
- Additional analgesic medication including dose and time of intake during the hospital stay

9.3.5 Hospital stay and follow up data (postoperative day 1 and 2, follow up 2-4 weeks, 3 and 6 months later)

Daily ward rounds until discharge by the surgeon and his delegates to assess the patient for complications. Follow up is performed by the surgeon and the study coordinator during the visit at our outpatient clinic or per telephone inquiry

- Date of discharge from the hospital (day/month/year)
- Pain intensity [VAS Score] – with coughing and when immobile
- Additional analgesic medication including dose and time/date of intake during the hospital stay

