11.4 Statistical criteria of termination of trial

No such criteria are defined.

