12.5 Confidentiality, Data Protection

The participants name or other personal identifiable data are not recorded in the CRF as well as study database. Each participant will be coded using a unique identifier (Patient-ID). The relation between Patient-IDs and personal identifiable data is recorded in a separate document which is restricted to the PI.

Direct access to source documents will be permitted for purposes of monitoring, audits and inspections (12.4)

The research team, CEC and CA will have access to the protocol.

The sponsor-investigator, PI and study coordinator will have access to the dataset, statistical code, etc. during and after the study.

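### A batch number on the prepared study drug can reveal the arm to treating staff, because lidocaine and NaCl are unmatched hospital stock; the label and access rules need tightening

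*Protocol*

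**What the plan says.** Section 8.1.3 states that, after randomisation, an anaesthesiologist or study nurse who is not taking part in the surgery "will label the IMPs with Patient ID and Chargen/Batchnumber on the day before surgery" and then keeps the product in a cooler until use. Section 6.2.2 describes the same step as preparation just before surgery "in syringes marked with patients study number", and section 8.8 repeats this. Neither 6.2.2 nor 8.8 mentions a batch number on the syringe.

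Section 8.8 calls lidocaine and NaCl standard products in general use at the hospital and available in the operating room. Section 2.2 says packaging will not be changed. Section 8.8 also has batch numbers archived in a dispensing log without naming the drug, as though a batch number did not identify it.

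On access, section 6.2.2 places the allocation in the EDC system. Section 6.3 says the anaesthesiologist or thoracic surgeon "can unblind each participant at any time by extracting the treatment assignment from the records in the EDC software". Section 12.5 says: "The sponsor-investigator, PI and study coordinator will have access to the dataset, statistical code, etc. during and after the study." Section 9.3.5 says: "Follow up is performed by the surgeon and the study coordinator during the visit."

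**The concern.** Blinding with two off-the-shelf products depends on nothing at the bedside telling one syringe from the other. A batch number does tell them apart. Staff could match it to stock in the operating room, or link it to an earlier patient whose arm is known. Section 8.1.3 thus works against safeguards that the protocol sets up elsewhere, such as the restricted accountability sheet.

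The primary endpoint combines pain VAS and morphine over 24 hours. VAS depends on how and when the question is put, PCA settings may be adjusted to the patient's need (9.2.1), and additional metamizol may be given (Synopsis). Staff who know or suspect the arm could influence each of these without intending to. The data-access wording is a lesser concern: it does not say that allocation is withheld from people who also collect data.

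**Working it through.** The protocol gives no figure on this point, so the check is a side-by-side reading followed by one conditional illustration.

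**Label.**
- 8.1.3: Patient ID plus batch number, applied the day before surgery.
- 6.2.2 and 8.8: study number, with preparation just before surgery.
- The sections differ on both content and timing. 8.1.3 speaks of IMPs rather than syringes. That the label is on the syringe is inferred from 6.2.2 and 8.8, where the marked item kept in the cooler until administration is the syringe.

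**What a batch number reveals.** The two products are separate stock (8.8) and are not repackaged (2.2). Each batch number therefore belongs to one product. Two syringes with the same number are in the same arm, however many batches are in use.

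**When it could matter.** The infusion runs until 2 hours after skin closure (8.2.1). VAS is scored at 1, 2, 4, 8, 16 and 24 h (9.2.1), and the average enters the SIA score (11.5.1). The 1 h score falls within the infusion and the 2 h score at its end: 2 of 6 time points, or one third of the average.

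**Access.**
- The allocation is in secuTrial (6.2.2), and users see what their permissions allow (12.2.2). The protocol does not say which roles may see the allocation.
- 12.5 grants access to the dataset during the study and does not say whether allocation is included.
- The coordinator collects perioperative data (9.3.3), including surgery duration and number of trocars, the two covariates of the primary model (11.5.1). The coordinator also takes part in the follow-up at which VAS is recorded (9.3.5). The protocol does not name who records the 24-hour VAS.

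**Illustration only.** Suppose there is no true effect, and knowledge of the arm shifts the between-arm VAS difference by d at the 1 h and 2 h scores and at no other time. The six-point average then shifts by b = 2d/6 = d/3. Take the SD of 1.91 (11.2) and 21 evaluable patients per arm (11.3):

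SE = 1.91 × √(2/21) = 0.589

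Rejection rate = Φ(b/SE − 1.96) + Φ(−b/SE − 1.96)

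| Assumed d at 1 h and 2 h | b | b/SE | Rejection rate of a two-sided 5% test on VAS |
|---|---|---|---|
| 0.75 | 0.25 | 0.42 | 7.1% |
| 1.5 | 0.50 | 0.85 | 13.6% |

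The values of d are assumptions, and the protocol gives none. The calculation concerns VAS alone, not the SIA score. It shows only that a shift confined to two readings would be diluted but would not vanish.

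**The case against.** The protocol clearly tries to protect the blind. The randomising person stays out of care and assessment (6.2.2), and the preparer does not take part in surgery. The accountability sheet is open only to a doctor outside care and assessment, and the amount infused is calculated later to avoid unblinding (9.3.3). Allocation revealed for a SUSAR is withheld from investigator and study staff (10.1.1). VAS is the patient's own rating, PCA requests are logged by the pump, and a batch number tells the patient nothing. Neither 6.2.2 nor 8.8 says that the study number is the only mark, so 8.1.3 may simply add detail.

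Most of this stands and limits the finding. It does not remove the label problem. Read as added detail, 8.1.3 still puts a product-specific number on the study drug. Traceability does not require it there, since the accountability record links patient to batch.

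Three stronger readings are tempting and are not supported.
- *The PI and coordinator can see the arm.* 12.5 does not say that the dataset contains it, and EDC viewing depends on permissions. The coordinator is tied to perioperative data and later follow-up, not to the 24-hour VAS.
- *The allocation is open to any surgeon or anaesthesiologist.* 6.3 is a code-break section. It lists indications and requires reporting and documentation.
- *Informal looks inflate the type I error.* Section 2.9 lists "early evidence of benefit or harm of the experimental intervention" as an example of a reason to terminate, and 11.4 says "No such criteria are defined". The protocol plans no repeated efficacy tests. The only interim analysis (11.3) was blind to arm labels and had arm means subtracted.

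**Conclusion.** The point holds in limited form. If 8.1.3 is followed as written, treating staff can come to see a number that identifies the product, and 6.2.2 and 8.8 do not match it. The blind is at risk during the infusion, which covers two of the six pain time points in the primary endpoint. A reader might infer that the double blind is broken or the primary result biased. The protocol supports neither, and the size of any bias is unknown.

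The conclusion assumes that the label is on the syringe or otherwise visible to staff giving care or scoring pain. It does not depend on how many batches are in use, although more batches would mean fewer patients linked by each number. The access wording in 12.5 and 6.3 is a gap to close, not evidence of unblinding.

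**What to change.** 1. In 8.1.3, mark the syringe with the patient study number only.
2. Keep batch numbers solely on the restricted drug accountability sheet held by the unblinded preparer. Put the dispensing log and Drug Accountability Log of 8.8 under the same restriction, since they also carry batch numbers.
3. Reconcile 6.2.2, 8.1.3 and 8.8 on label content and on when the product is prepared and labelled.
4. In 12.5, state that any dataset available to the sponsor-investigator, PI or coordinator before database lock excludes treatment allocation and batch number.
5. In 6.3, state that viewing the allocation in secuTrial is limited to the unblinded preparer and the documented emergency code break.

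The cost is a changed label template, one EDC permission setting and short wording changes. Batch traceability and emergency unblinding both remain available.
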